16.1.2 TEAEs Leading to Discontinuation of Study Device

All TEAEs leading to permanent discontinuation of medical device will be identified by "Action taken with study device" variable collected on the Adverse Events page of the eCRF and completed as "device withdrawn".

Document:	Y:\Kimberly-Clark\DryNites\Documentation\SAP\DryNites_SAP_v1.0_20200203		
Author:	[name]	Version Number:	1.0
		Version Date:	03Feb2020
Template No.: I	RWI_TP_BIOS0013 Revision 1		Reference: RWI_WI_BIOS0015

Effective Date: 15Jun2018

For TEAEs leading to discontinuation of study device, summaries of incidence rates (frequencies and percentages) by SOC and PT will be prepared. In case of less than 5 events occurred, a listing only will be provided.

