# 4 METHODOLOGY

# 4.1. Study Design

This is an 8-week randomised, open-label, 2-arm, parallel-group Phase IV trial with a 2:1 allocation ratio for discontinuation of continuation of use of DryNites® absorbent pants in children with NE, with an optional 4-week extension period. This will be an equivalence trial for the primary endpoint.

Eligible patients are children with monosymptomatic NE, not previously treated for NE, and managed with absorbent pants/nappies (any brand) for a minimum of 6 months. Participants must be dry at day for at least 6 months. Participants will be divided in 2 age groups of similar

size. The younger age group will be comprised of participants aged 4-<6 years old and the older age group will be comprised of participants aged  $\ge 6-8$  years old. Capping of the faster recruiting subgroup will be implemented if needed.

Participation in the study will be proposed for all children meeting the above conditions; parents/carers should be given sufficient time to review the study information and provide informed consent to their child's and their participation. Children's assent will be requested for the older age group.

The study consists of 3 consecutive periods of 4 weeks each, including the run-in, the intervention (core trial) period, and the extension period.

Participant meeting the eligibility criteria will enter the run-in period. During the 4-week run-in period, all participants will be assigned to using DryNites® every night.

Participant meets the inclusion criterion of NE 7 nights per week during the last week of the run-in period will be randomised to participate in the intervention (core trial) period. During the 4-week intervention period, participants will be assigned to either stopping the use of absorbent pants or continuing DryNites® in a 2:1 ratio. All participants will receive absorbent bed mats to use every night, however, the use of bed mats is optional.

Following completion of the 4-week intervention period, participants will be invited to participate in the optional 4-week extension. During the optional 4-week extension period, participants will remain on their randomly assigned treatment for an additional 4 weeks.

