# 4.3.5. Methods for Assigning Patients to Treatment Groups

A patient randomisation list will be produced using permuted block randomisation stratified by age group (4–<6 years old and  $\ge6-8$  years old) and a 2:1 group allocation for discontinuation or continuation of the use of DryNites® pyjama pants.

When a patient is qualified for entry into the randomised treatment period, treatment assignment will be performed by means of an IWRS on a central level on Visit 2 (Day  $28 \pm 7$  days).

Before the study is initiated, the log in information and directions for the IWRS will be provided to each study centre.

The Investigator or his/her delegate (study coordinator) will log on to the EDC and confirm that the patient fulfils the eligibility criteria and proceed with the randomisation. Participants will be assigned a unique number (randomisation number) in ascending numerical order on the next available record in the group at each study centre. The randomisation number encodes the participant's assignment to 1 of the 2 arms of the study (No Pants arm or DryNites® arm).

The treatment assignment (Discontinuation vs. continuation of DryNites®) will be captured in the EDC from the IWRS.

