#### 4.3.6. Patient Withdrawal and Discontinuation of Study Treatment

Any individual participant will be withdrawn from the study if any of the following criteria apply:

- Withdrawal of parents/carers consent, for any reason
- Investigator's decision
- Adverse event (AE)
- Initiation of a prescribed therapy for NE (pharmacologic or bed alarm)

- Severe non-compliance with the study clinical investigation plan, including deviations to eligibility criteria and non-compliance with the study procedures
- Participant's death
- Participant lost to follow-up

Parents/carers may withdraw consent and discontinue the patient's participation in the study at any time, for any reason with no effect on their medical care or access to treatment. If consent is withdrawn prior to completing the study core and/or extension period, the parents/carers will always be asked about the reason(s) and the presence of any AEs. Any known reason for withdrawal should be documented in the electronic case report form (eCRF). The Investigator will follow-up AEs outside of the clinical study.

If a participant is withdrawn from participation in the study, then his/her enrolment code cannot be reused. Withdrawn participants will not be replaced.

All information already collected as part of the study will be retained for analysis; however, no further efforts will be made to obtain or record additional information regarding the participant. The Investigator may discontinue a participant from the study treatment at any time if the Investigator considers it necessary, due to medical reasons, ineligibility (either arising during the study or retrospectively having been overlooked at screening), significant deviation from the clinical investigation plan, significant non-compliance with study requirements.

The Investigator should document any deviation from the clinical investigation plan regardless of their reasons.

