# **4.4.2.** Provision of Study Treatment

DryNites®, defined as the study treatment, is commercially available medical device of Class I and will be provided free of charge to the study participants. DryNites® should be used in accordance to this clinical investigation plan instructions. Study treatment and absorbent bed mats will be supplied to the participants by the Investigator/site; however, the use of bed mats is optional. A 4-week supply will be distributed to each participant's parents/carers at each visit Day 0, Day  $28 \pm 7$  days, and Day  $56 \pm 7$  days. In case of remote visits, study materials will be shipped by the site to the patient's address according to local law and regulatory instructions. All packages will be labelled "for use in clinical investigation only" (in the applicable local languages).

The younger age group will be provided with the 4–7 years DryNites® size. Parents/carers in the older age group will select whether age 4–7 or age 8–15 DryNites® size is most appropriate. DryNites® age 4–7 years are provided in packs of 10. As such, each participant will be provided with 4 packs of DryNites® to cover each 4-week period.

DryNites® age 8–15 years are provided in packs of 13. As such, each participant will be provided with 3 packs of DryNites® to cover each 4-week period.

Absorbent bed mats are provided in packs of 12. Each participant randomised in the intervention group (discontinuation of DryNites® pants) will be provided with 3 packs of bed mats to cover each 4-week period. Participants randomised in the control group (continuation of DryNites® pants) will receive 1 pack of bed mats per 4-week period. The use of bed mats is optional.

Any surplus of DryNites® and absorbent bed mats at the end of each 4-week period can be kept by the participant.

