## 7.2. Procedures for Reporting Adverse Events in the Case Report Form

All AEs (serious and non-serious) reported during the study period (from signature of the ICF until study discontinuation) will be captured on the appropriate study CRF.

Each suspected AE occurring during the study must be recorded in the appropriate CRFs and/or specific AE forms as designated by the Sponsor, including the description, seriousness criteria, severity, duration (onset and resolution date), causal relationship with the study device, actions taken with the study device any other required treatment, and outcome.

The following variables will be collected for each AE:

- AE (verbatim)
- Start and stop dates
- Event severity
- Seriousness
- Relationship with the study device
- Action taken with regard to the study device
- Outcome of the AE
- AE caused patient's withdrawal from study (yes or no)

In addition, the following variables will be collected for SAEs:

- Date AE met criteria for SAE
- Date Investigator became aware of SAE
- Criteria for seriousness
- If relevant: date of hospital admission and discharge
- If relevant: date and probable cause of death

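### The only summary of AEs leading to discontinuation selects on device withdrawal, so after randomisation it captures such events essentially only in the DryNites arm

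*SAP*

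**What the plan says.** SAP 16.1.2 is headed for TEAEs leading to discontinuation of the study device. Its selection rule is: "All TEAEs leading to permanent discontinuation of medical device will be identified by" the device-action variable on the AE page when it reads device withdrawn. On the output it says: "For TEAEs leading to discontinuation of study device, summaries of incidence rates (frequencies and percentages) by SOC and PT will be prepared". With fewer than 5 events, only a listing is produced. Nothing else in SAP section 16 concerns AEs that lead to discontinuation of any kind.

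The device is the pants: "DryNites®, defined as the study treatment, is commercially available medical device of Class I" (Protocol 4.4.2). After the run-in, "participants will be assigned to either stopping the use of absorbent pants or continuing DryNites® in a 2:1 ratio" (Protocol 4.1).

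Leaving the study because of an AE is possible in either arm. Protocol 4.3.6 begins "Any individual participant will be withdrawn from the study if any of the following criteria apply" and lists an AE among the criteria, without distinguishing arms. Protocol 7.2 collects two separate items for each AE: the action taken with the device, and whether the AE caused the patient's "withdrawal from study (yes or no"). The SAP text uses the first and does not mention the second.

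**The concern.** The selecting variable depends on having a device to withdraw. In the no-pants arm the assignment itself removes the device at randomisation, so a later AE that leads a family to leave the study has no natural route to that value. In the DryNites arm the route exists. The output is therefore sensitive to AE-driven discontinuation in one arm and nearly blind to it in the other, and the blind arm is the larger one and the one receiving the tested intervention.

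The rule can also miss events in the DryNites arm. An AE that ends study participation without being coded as device withdrawn is not selected. Device action and study withdrawal are different facts, and the protocol records them separately.

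At stake is how one safety output is interpreted. If it were set out by arm, an absence of post-randomisation entries under no pants would follow from the design and would say nothing about how many children left because of an AE.

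**Working it through.** **Allocation share.** Protocol 4.3.5 specifies "2:1 group allocation for discontinuation or continuation of the use of DryNites® pyjama pants". The no-pants share is 2/(2+1) = 0.667. The sample-size section applies the same ratio: 15 in the continuation arm gives 3 × 15 = 45 per age group, of whom 30 are in the no-pants arm, and 30/45 = 0.667. The point does not depend on the power calculation.

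**Number of children.** Protocol 4.3 aims to randomise about 120. Then 120 × 2/3 = 80 have no assigned device after randomisation and 40 keep it. Protocol 5.2 reaches 120 by adding an allowance for dropouts and run-in screen failures to 45 per age group. If only 2 × 45 = 90 were randomised, the split would be 60 and 30. The two-thirds share is the same.

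**Denominator and numerator.** SAP 6.3 places every child exposed to DryNites for at least 1 night after consent in the Safety Set, and all children are assigned DryNites in the run-in. No-pants children are therefore in the safety denominator, but after randomisation they have essentially no way into this numerator. Protocol 7.1.5 recognises the same feature for a neighbouring variable: relationship to DryNites is not applicable in the arm that stops the pants. SAP 16.1.2 makes no matching provision for device action.

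**Run-in.** SAP 16.1 counts TEAEs from the start of screening, so a run-in event in any child can be coded as device withdrawn. The gap is confined to the period after randomisation.

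**What the rule would capture.** The documents give no rate of AE-driven withdrawal. Assume a rate r that is equal in the two arms, one event per child, post-randomisation events only, and every such event in the DryNites arm coded as device withdrawn. Expected events are 80r in the no-pants arm and 40r in the DryNites arm, so the share missed is 80r/120r = 2/3 for any r.

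| Assumed r | No pants (80r) | DryNites (40r) | Captured by the current rule | Captured by the withdrawal item |
|---|---|---|---|---|
| 2% | 1.6 | 0.8 | 0.8 of 2.4 | 2.4 of 2.4 |
| 5% | 4 | 2 | 2 of 6 | 6 of 6 |
| 10% | 8 | 4 | 4 of 12 | 12 of 12 |

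**Effect of the fewer-than-5 rule.** All three captured counts under the current rule (0.8, 2 and 4) are below 5, so the output would be a listing without percentages. To reach a table, post-randomisation events in the DryNites arm alone would need a rate of 5/40 = 12.5%. Run-in events could add to the count, but they arise before the arms differ. Selecting on the withdrawal item would reach 5 events over both arms at 5/120 = 4.2%.

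**The case against.** The strongest reply is that SAP 16.1.2 does what its heading says. It is about stopping the device, and device action is the right variable for that. Protocol 5.4.4 does not ask for a summary of AEs leading to study withdrawal, so the SAP does not depart from the protocol. This stands: the defect is an absent companion output, not a wrong rule.

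Two stronger readings are tempting, and the documents do not support either.

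- A reader might infer that the report will show a table with no withdrawals under no pants against several per cent under DryNites. At the rates assumed above the fewer-than-5 rule gives a listing, and SAP 16.1.2 does not itself say that its summary is split by arm.
- A reader might infer that the tolerability of stopping the pants goes unreported. SAP 16.1 tabulates TEAEs and serious TEAEs for each group by SOC and PT, whether or not they lead to withdrawal. SAP section 10 reports time and reasons for discontinuation, with the randomised patients of each treatment group as denominator. SAP section 7 lists individual data for the Screened Set.

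Other caveats also stand. The eCRF response options are not shown, and a no-pants child wearing pants against the plan (SAP 6.4 anticipates this) might be coded as device withdrawn. The output templates mentioned in SAP section 9 are not among the documents, so an output using the withdrawal item may exist there. The SAP plans no confirmatory testing, and its safety objectives are descriptive.

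These replies do not supply what is missing. Disposition gives a reason without the event term. The TEAE tables give terms without the withdrawal. A listing leaves the reader to join the two by hand. An unsplit version of 16.1.2 would still omit the same children.

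**Conclusion.** The point holds as a gap in safety reporting. The only described summary of AEs leading to discontinuation uses a variable that, after randomisation, is meaningful essentially only in the DryNites arm. About 80 of 120 randomised children, two thirds at any sample size, have no assigned device to withdraw, so the output should not be read as a between-arm comparison. No described output links AE terms to study withdrawal in both arms, although the item needed is collected.

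The share follows from the 2:1 ratio. That two thirds of AE-driven withdrawals would be missed rests in addition on the assumptions of equal rates and complete coding in the DryNites arm. That the no-pants arm contributes almost nothing is inferred from the design, since the eCRF options are unseen. No primary, secondary or overall safety conclusion changes.

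**What to change.** In SAP 16.1.2, add a summary by SOC and PT of TEAEs for which the AE-page item on withdrawal from the study is Yes, or a listing if there are fewer than 5 events. Present post-randomisation events by randomised arm and run-in events separately. Use this output for any comparison of AE-driven withdrawal between arms.

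Keep the device-withdrawn output, with a label stating that it applies only to periods when DryNites are assigned: the run-in for all children, and the time after randomisation for the continuation arm.

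The cost is one extra output and a short SAP edit. Protocol 7.2 already provides for collecting the data, and sample size and the primary analysis are unaffected.

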16.1.3 Serious Adverse Events

Serious adverse events (SAEs) are those events recorded as "Serious" on the Adverse Events page of the eCRF. A summary of serious TEAEs by SOC and PT will be prepared. In case of less than 5 events occurred, a listing only will be provided.

16.1.4 Adverse Events Leading to Death

The TEAEs leading to death are those events which are recorded as "Fatal" on the Adverse Events page of the eCRF. A summary of TEAEs leading to death by SOC and PT will be prepared. In case of less than 5 events occurred, the events will be identified by the listing of serious adverse events.

16.1.5 Medical Device Incident

Medical Device Incident will be identified by "Is this event considered a Medical Device Incident (MDI)" variable collected on the Adverse Events page of the eCRF and completed as "Yes". A summary of MDI by SOC and PT will be prepared. In case of less than 5 events occurred, the MDI will be listed only.

16.2 Deaths

If any patient dies during the study as recorded on the AE page of the eCRF, the information will be identified by the SAE listing only.

Document:	Y:\Kimberly-Clark\DryNites\Documentation\SAP\DryNites_SAP_v1.0_20200203			
Author:	[name]	Version Number:		1.0
		Version Date:		03Feb2020
Template No.:	RWI_TP_BIOS0013 Revision 1	F	Reference:	RWI_WI_BIOS0015
Effective Date:	15Jun2018			

Page 34 of 38

16.3 Laboratory Evaluations

Not applicable.

16.4 Vital Signs

Not applicable.

16.5 Physical Examination

The following summaries will be provided for physical examination data performed at Visit 1 on SCR and RND Set (overall and by age groups):

- Incidence of abnormalities overall (at least one abnormalities);
- Incidence of abnormalities upon external genitalia examination of urethral meatus, overall and for each available pre-specified condition (hypospadias; meatal stenosis; phimosis; labial adhesions, other);
- Incidence of abnormalities upon examination of the lower back overall and for each available pre-specified condition (dimples, hypertrichosis, suspect palpatory finding, other);
- Incidence of abnormalities upon orienting neurological examination and inspection of the feet;
- Incidence of abnormalities upon grasp function of the toes tested for an intact S1-S2-S3 innervation;

17.1 APPENDIX 1. Partial Date Conventions

Imputed dates will NOT be presented in the listings.

ALGORITHM FOR TREATMENT EMERGENCE OF ADVERSE EVENTS:

START DATE	STOP DATE	ACTION	
Known	Known	If start date < screening date, then not TEAE	
		If start date >= screening date, and <= End of extension period, then TEAE	
	Partial	If start date < screening date, then not TEAE	
		If start date >= screening date, and <= End of extension period, then TEAE	
	Missing	If start date < screening date, then not TEAE	
		If start date >= screening date, and <= End of extension period, then TEAE	
Partial, but known components show that it cannot be on or after randomisation	Known	Not TEAE	
	Partial	Not TEAE	
	Missing	Not TEAE	

Document:	Y:\Kimberly-Clark\DryNites\Documentation\SAP\DryNites_SAP_v1.0_20200203		
Author:	[name]	Version Number:	1.0
		Version Date:	03Feb2020
Template No.	RWI_TP_BIOS0013 Revision 1	Reference: I	RWI_WI_BIOS0015

Effective Date: 15Jun2018

START DATE	STOP DATE	ACTION
Partial, could be on or after	Known	If stop date < screening date, then not TEAE
screening		If stop date >= screening date, and <= End of extension period, then TEAE
	Partial	Impute stop date as latest possible date (i.e. last day of month if day unknown or 31st December if day and month are unknown), then:
		If stop date < screening date, then not TEAE
		If stop date >= screening date, and <= End of extension period, then TEAE
	Missing	Assumed TEAE
Missing	Known	If stop date < screening date, then not TEAE
		If stop date >= screening date, and <= End of extension period, then TEAE
	Partial	Impute stop date as latest possible date (i.e. last day of month if day unknown or 31st December if day and month are unknown), then:
		If stop date < screening date, then not TEAE
		If stop date >= screening date, and <= End of extension period, then TEAE

Document: Author: Version Number:

1.0

Version Date:

03Feb2020

Template No.: RWI_TP_BIOS0013 Revision 1

[name]

Reference: RWI_WI_BIOS0015

Effective Date: 15Jun2018

Page 38 of 38

START DATE	STOP DATE	ACTION
	Missing	Assumed TEAE

TEAE: Treatment emergent adverse event

Document:	Y:\Kimberly-Clark\DryNites\Documentation\SAP\DryNites_SAP_v1.0_20200203		
Author:	[name]	Version Number:	1.0
		Version Date:	03Feb2020
Template No.: F	RWI_TP_BIOS0013 Revision 1		Reference: RWI_WI_BIOS0015

Effective Date: 15Jun2018

Statistical Analysis Plan - SAP - 13-Feb-2020

Electronic Signature Manifestation

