## 5.4.4. Safety Analyses

All safety analyses will be performed on the Safety Analysis Set.

AEs are reported since ICF signature, throughout the patients' discontinuation of the study.

Treatment-emergent adverse events (TEAEs) are defined as AEs that first occurred or worsened in severity after randomisation and prior to the end of the extension period.

AEs that occurred from ICF signature till randomisation will be described separately.

AEs will be coded using MedDRA. For each group, numbers and proportion of TEAEs, device-related TEAE and serious TEAEs will be tabulated by SOC and PT.

Medical Device Incidents not associated with a TEAE will be described separately.

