4.3 Changes to Analysis from Protocol

Concomitant medications will be collected in relation to adverse events and medical device incidents only. For this reason, the summary of concomitant medication will be provided on randomised analysis set only as no data will be collected for patients screened and not randomised.

Document:	Y:\Kimberly-Clark\DryNites\Documentation\SAP\DryNites_SAP_v1.0_20200203		
Author:	[name] Version Number:		1.0
		Version Date:	03Feb2020
Template No.: RWI_TP_BIOS0013 Revision 1			Reference: RWI_WI_BIOS0015
Effective Date: 15Jun2018			

Safety set definition will be modified to include all patients exposed to DryNites for at least 1 night after signature of informed consent.

Treatment emergent adverse events will be defined as all events occurred or worsened in severity after the start of the screening period.

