16.1 Adverse Events

Adverse Events (AEs) will be coded using the version of MedDRA available at the time of the analysis.

Treatment emergent adverse events (TEAEs) are defined as AEs that first occurred or worsened in severity after the start of screening period and prior to the end of the extension period.

See Appendix 1 for handling of partial dates for AEs. In the case where it is not possible to define an AE as treatment emergent or not, the AE will be classified by the worst-case scenario; i.e. treatment emergent.

The AEs that occurred from ICF signature till randomisation will be described separately and presented in a listing.

For each group, numbers and proportion of TEAEs, device-related TEAE and serious TEAEs will be tabulated by SOC and PT along with number of events.

Medical Device Incidents (MDI) not associated with a TEAE will be described separately in a listing.

Document:	Y:\Kimberly-Clark\DryNites\Documentation\SAP\DryNites_SAP_v1.0_20200203		
Author:	[name]	Version Number:	1.0
		Version Date:	03Feb2020
Template No.: I	RWI_TP_BIOS0013 Revision 1		Reference: RWI_WI_BIOS0015

Effective Date: 15Jun2018

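### One row of the SAP's partial-date rule for adverse events is anchored on randomisation instead of screening, so some run-in events can be classed as not treatment-emergent although the same event with a full date is a TEAE

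*SAP*

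**What the plan says.** The protocol (5.4.4) defines TEAEs as "AEs that first occurred or worsened in severity after randomisation and prior to the end of the extension period". The SAP changes this openly. Section 4.3 states: "Treatment emergent adverse events will be defined as all events occurred or worsened in severity after the start of the screening period". Section 16.1 repeats the new anchor: "AEs that first occurred or worsened in severity after the start of screening period and prior to the end of the extension period". Section 16.1 also sets a default for events whose status cannot be settled: "the AE will be classified by the worst-case scenario; i.e. treatment emergent".

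SAP Appendix 1 (17.1) turns the definition into a table.

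- Start date known: not a TEAE if before screening; otherwise "If start date >= screening date, and <= End of extension period, then TEAE".
- Start date partial, first row: "Partial, but known components show that it cannot be on or after randomisation". The action is Not TEAE for a known, a partial and a missing stop date.
- Start date partial, companion row, for starts that may be on or after screening: not a TEAE if the stop date precedes screening; otherwise "If stop date >= screening date, and <= End of extension period, then TEAE". A partial stop date is first imputed to its latest possible value. A missing stop date means the event is assumed to be a TEAE.
- Start date missing: the same actions as the companion row.

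Every row except the first partial-start row compares a date with screening or assumes TEAE.

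**The concern.** The odd row carries the anchor of the protocol definition that SAP 4.3 replaced, and nothing in the SAP gives a reason for a separate anchor there. It reads like text left over when the definition was changed, though that is an inference.

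Two things follow. Whether a run-in event counts as a TEAE can depend on how completely its start date was recorded. And an event can meet two rows with opposite actions, so a programmer has to choose.

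The run-in is a period of device exposure: all participants are assigned DryNites® every night (Protocol 4.1). For children later randomised to stop, two-thirds of those randomised under 2:1 allocation, it is also the only period in which relationship to the device is assessed (Protocol 7.1.5). What is at stake is the completeness of the TEAE tables for that period.

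**Working it through.** The SAP states no figure here to reproduce. The check applies the Appendix 1 rows to the same event with and without its day of onset.

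**Worked example** (illustrative dates). Screening 5 March, randomisation 28 days later on 2 April, onset 10 March.

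- Full date: 10 March is on or after 5 March, so the event is a TEAE.
- Day missing, first partial row: the latest possible start is 31 March, before 2 April, so the event is Not TEAE.
- Day missing, companion row: March can include dates on or after 5 March, so this row applies too. It gives TEAE for any stop date from 5 March to the end of the extension, and assumes TEAE if the stop date is missing.

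**Length of the window.** Visit 2 is at Day 28 ± 7, so the run-in lasts 28 − 7 = 21 to 28 + 7 = 35 days (3 to 5 weeks). The one-week re-screening run-in in Protocol 4.3.4 takes it to 35 + 7 = 42 days (6 weeks).

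**Share of run-in onsets caught.** Assumptions: screening dates spread evenly over a 365-day year, onset equally likely on each run-in day, and only the day missing. With a 28-day run-in there are 365 × 28 = 10,220 combinations of screening date and onset day. One is caught when the onset month ends before randomisation. Around each month-end the number of such combinations is 1 + 2 + … + 28 = 28 × 29 / 2 = 406, so over 12 months 12 × 406 = 4,872.

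| Run-in | Combinations | Caught | Share |
|---|---|---|---|
| 21 days | 365 × 21 = 7,665 | 12 × 231 = 2,772 | 36.2% |
| 28 days | 10,220 | 4,872 | 47.7% |
| 35 days | 365 × 35 = 12,775 | 7,402 | 57.9% |

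(At 35 days the run-in is longer than any month, so the simple sum no longer applies; 7,402 comes from direct enumeration.)

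Every event caught would be a TEAE with a full date. Every one also meets the companion row's condition, because the true onset is on or after screening and so the recorded month must allow it.

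**Where the worst-case default applies.** The default covers only events whose status cannot be determined. Of the 4,872 caught at 28 days, a month lying wholly within the run-in occurs only for February with screening on 1 February: 28 onsets, 28 / 10,220 = 0.3%. Those are plainly TEAEs under 16.1 and need no default. The other 4,872 − 28 = 4,844 could fall on either side of screening, and there the row contradicts the default.

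**Children never randomised.** The Safety Analysis Set (SAP 6.3) takes in anyone exposed for at least one night after consent. That includes children who fail at the end of the run-in (Protocol 4.3.4). They have no randomisation date to compare with.

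**After re-anchoring the row on screening.** None of the 10,220 combinations falls in it. All go to the companion row, and the two rows no longer overlap.

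**The case against.** The strongest reply has three parts.

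First, the events are not lost. SAP 16.1 lists adverse events from consent to randomisation separately, and 16.1.1 summarises all adverse events alongside TEAEs. Medical device incidents are identified by their own eCRF item (16.1.5). Run-in events also precede randomisation, so they say nothing about the comparison between arms. This stands, and it confines the harm to TEAE-based tables.

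Second, the table is ambiguous rather than certain to give the wrong class, since the companion row also applies. This stands too. A reader might infer a systematic, one-directional loss of TEAEs. The documents do not support that, because no precedence is stated and a programmer could apply the companion row. But a rule that allows both answers is still defective.

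Third, the row agrees with the protocol, whose later version 3.0 (January 2022, against SAP version 1.0 of February 2020) keeps the post-randomisation definition. On this view the real question is which definition governs. That bears on which correction to make. It does not rescue the SAP, which adopts screening in 4.3 and 16.1 and uses it in every other date comparison in Appendix 1.

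**Conclusion.** The row is wrong as written, and the defect is minor. It conflicts with SAP 4.3 and 16.1, overlaps the companion row, conflicts with the worst-case default where the date could fall on either side of screening, and cannot be evaluated for exposed children who were never randomised.

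A reader might infer that every run-in event with a partial start date becomes non-emergent. That goes too far: a date in the randomisation month does not exclude randomisation or later, so it goes to the companion row. The shares of 36% to 58% for run-ins of 21 to 35 days rest on the even-spread, day-only-missing assumptions. They are shares of partial-date events, not of all adverse events. The documents give no rate of partial dates; the absolute number is probably small.

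The effect is limited to tables built on TEAE status (all, related and serious TEAEs). The primary analysis is unaffected.

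**What to change.** In that Appendix 1 row, replace randomisation with screening. This is a one-word change that brings every row into line with SAP 4.3 and 16.1, removes the overlap, and makes the row usable for children who were never randomised.

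If the sponsor prefers to restore the protocol's post-randomisation definition, the edit is larger: re-anchor all the other rows, and the definitions in SAP 4.3 and 16.1, on randomisation. Either change is to SAP text and the derivation program only and needs no new data. It should be made before the safety tables are programmed.
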